# 7.7. Concomitant Treatment and Supportive Care Guidelines

There is a potential for interaction of cobimetinib with other concomitantly administered drugs through the cytochrome P450 system, and should not be used with strong inhibitors or inducers of CYP3A4. The case report form must capture the concurrent use of all other drugs, over-thecounter medications, or alternative therapies. Patients taking any of the prohibited medications on the Prohibited Medications list are excluded from entering the study. This list can be found in the supplemental packet. Patients already enrolled in the study that initiate and persist taking any of the medications on the Prohibited Medications list (except for weak inhibitors) will be discontinued from the study. No apparent drug interactions have been identified for idasanutlin, but strong inhibitors and/or inducers of CYP2C8 and CYP3A4/5 may affect idasanutlin exposure. For idasanutlin, CYP2C8 inhibitors should be avoided when CYP3A4 inhibitors are allowed, since the risk of simultaneous administration of CYP3A4 and CYP2C8 inihibitors is unknown.

Patients on chronic medications that can be given concomitantly with Cobimetinib or Idasanutlin should be maintained on the same dose and dose schedule throughout the study period, as medically feasible. Caution should be used in patients on antiplatelet or anticoagulant therapy due to the risk of bleeding with cobimetinib. The investigator should instruct the patient to notify the study site about any new medications he/she takes after the start of the study drug. All medications (other than study drug) and significant non-drug therapies (including physical therapy and blood transfusions) administered after the patient starts treatment with study drug, and any changes in dosing should be recorded.

All supportive measures consistent with optimal patient care can be given throughout the study at the discretion of the treating physician, as long as they are not part of the list of prohibited medications (located in the supplemental packet). In general, the use of any concomitant medication/therapies deemed necessary for the care of the patient is permitted with the following considerations:

- □ Prophylactic anti-emetics should be started only once the patient experienced nausea or vomiting at the discretion of the investigator.
- G-CSF support will be allowed at the treating physician's discretion. Hematopoietic growth factors may be used according to ASCO guidelines (when applicable, we would suggest pegfilgrastim 6 mg subcut on Day 6 of the cycle for the idasanutlin arm; and filgrastim 300 -480 mcg subcut [based on body weight] on days 22, 23 and 24 of the cycle for the cobimetinib
- Bone directed therapy to prevent skeletal related events (SRE's) or to treat osteoporosis with bisphosphonates or denosumab is permitted. While the use of bisphosphonates has been found to reduce the incidence of new bone metastases in patients with metastatic breast cancer, we do not anticipate this to affect the results of this trial. Thus, treatment initiated prior to registration or after registration with these agents is permitted. The time of initiation of bone directed therapy should be clearly recorded on the case report forms
- Local radiotherapy required for life-threatening situations (e.g., superior vena cava syndrome, spinal cord compression, central nervous system metastases) will require the patient to discontinue protocol treatment due to symptomatic deterioration. However, limited palliative radiotherapy (i.e., to bone metastasis) in subjects who are otherwise benefiting from study treatment will be allowed during the study but must be discussed with the Protocol Chair. Study treatment should be withheld until palliative radiotherapy is terminated. This treatment break should not be considered as treatment interruption. Palliative radiation is permitted if done solely for bone pain relief. It should not be delivered to a target lesion and it should not encompass more than 25% of irradiated bone marrow. If palliative radiotherapy is initiated

after the start of study treatment, the reason for its use must be clearly documented and progression as per RECIST 1.1 must be ruled out Other investigational therapies must not be used while the patient is on the study Anticancer systemic therapy other than the study treatments must not be given to patients while on the study. If such agents are required for a patient then the patient must be discontinued from the study Herbal preparations are not allowed throughout the study. These herbal preparations include, but are not limited to: St. John's wort, Kava, ephedra (ma huang), gingko biloba, dehydroepiandrosterone (DHEA), yohimbe, saw palmetto, and ginseng. Patients should stop using these herbal preparations 7 days prior to first dose of study drug 7.8. Duration of Therapy Duration of therapy will depend on individual response, evidence of disease progression and tolerance. In the absence of treatment delays due to adverse events, treatment may continue until one of criteria in Section 7.11 applies. 7.9. Duration of Follow-Up Patients will be followed until 28 days (± 7days) following discontinuation of study treatment due to disease progression Patients removed from study treatment for unacceptable treatment related adverse event(s) will be followed weekly until resolution or stabilization of all treatment related adverse events to Grade 1 or lower Patients who have discontinued study treatment for any reason other than disease progression will be followed until disease progression 7.10. Criteria for Removal from Study Participants will be removed from study treatment when any of the criteria listed in Section 7.11 applies. All patients who initiate protocol treatment will be included in the safety analysis, and all patients who initiate protocol treatment and receive at least 8 weeks of treatment will be included in overall evaluation of response. All reasons for discontinuation of therapy should be documented clearly in the medical record. **Discontinuation of Treatment** 7.11. The reasons for discontinuation or protocol treatment include: Evidence of disease progression during treatment as deemed by the treating investigator □ Non-compliance with the study protocol, including, but not limited to not attending the majority of scheduled visits. The Protocol Chair will determine when non-compliance should lead to removal from study. Note: These patients will still be included in the overall evaluation of safety and response Unacceptable major toxicity. Note: These patients will still be included in the overall evaluation of safety and response

treatment

Intercurrent illness or condition that would, in the judgment of the treating investigator, affect assessment of clinical status to a significant degree or require discontinuation of study

- At subject's own request. Note: The reason for discontinuation from the study must be documented. These patients will be included in the overall evaluation of safety and response if any protocol therapy was administered prior to withdrawal
- Study is closed for any reason (e.g. new information shows that the patient's welfare would be at risk if she continued study treatment)
- General or specific changes in the participant's condition render the participant unacceptable for further treatment in the opinion of the treating investigator
- □ Patients that require a dose delay of > 28 days. If the delay is due to a cause unrelated to study participation, the patient will have the opportunity to continue study if beyond the first 8 weeks of treatment, if clinical benefit is seen, and if deemed eligible to do so by the Protocol Chair of the study
- ☐ If the patient requires dose reduction below dose level -1, the patient should be discontinued from the study unless deemed to have clinical benefit that would outweigh the risk. A discussion with the Protocol Chair should be carried out prior to final decision on discontinuation

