#### 7.12. **Replacement of Patients Who Discontinue Early**

In general, the study intends that patients would be treated until disease progression or intolerable toxicity. If a patient discontinues study treatment for reasons clearly not related to study treatment, after completing fewer than one planned cycle of study, and/or receiving <75% of the total intended dose of study drugs over the first cycle of treatment, then that patient will be considered not evaluable for efficacy analysis (will still be included in the safety analysis though) and may be replaced with a new patient.

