#### 12.1. **Definitions**

Evaluable for toxicity: All patients will be evaluable for toxicity from the time of their first administration of study treatment drugs.

Evaluable for objective response: Only those patients who have measurable disease present at baseline, have received at least one cycle of therapy, and have had their disease re-evaluated will be considered evaluable for response. These patients will have their response classified according to the definitions stated below.

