≤1 out of 6 at highest dose level below the maximally administered dose	This is generally the MTD and RP2D. At least 6 patients must be entered at the recommended phase 2 dose. These patients will also be considered evaluable in the phase II portion of the study.

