#### 24.3. Sample Size/ Accrual Rate

## 24.3.1. Primary Endpoint/ Sample Size

In recently reported trials of PD-L1 therapies, the median progression-free survival (PFS) rates of 8 weeks were observed in ER+ mBC. Assuming an exponential survival model, this corresponds to the hazard rate of 0.0866 and progression-free survival of 25% and 13% at 16 and 24 weeks, respectively. For the new treatment arms, we expect the median PFS to be 16 weeks, which corresponds to the hazard rate of 0.0433. The table below summarizes the two survival curves.

Group	Median	Hazard Rate	Proportion Surviving		
	Survival		8 weeks	16 weeks	24 weeks
Historical Control	8 weeks	0.0866	50%	25%	13%
Cobimetinib / Idasanutlin	16 weeks	0.0433	71%	50%	35%

Our proposed phase II trial results will serve as a proof-of-concept for future immunotherapy combination strategies in these patients. In view of the overall low PFS in ER+ mBC treated with single-agent immune checkpoint inhibitors, we opted for an open-label design without an Atezolizumab only control arm, and will use the 16-week PFS (Yes/No) as the primary endpoint. "Response" (16-week PFS and 8-week PFS) will be estimated and reported along with a 95% exact confidence interval. Progression-free survival will be estimated using the Kaplan-Meier method with censoring used as needed (e.g. if a patient is lost to follow-up, or analysis is done before all patients have had the event of interest). Median time to event and corresponding 95% CI will be reported along with Kaplan-Meier curves. The duration of PFS for patients who progress and then subsequently die will be the number of days between initiation of the study treatment and the date of when disease progression is first observed.

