We propose to use a Simon's Minimax design with stage I and II sample sizes of 16 and 17. respectively (maximum total of 33 patients per arm), to ensure that the total number of patients exposed to Atezolizumab + Cobimetinib or Idasanutlin is minimized in each of the arms in the trial. The futility boundary at the end of stage I is 4, that is if we have 4 of fewer "responses", then the trial will be terminated. At the end of the trial if there are 13 or more "responses", we will conclude clinical benefit of Cobimetinib or Idasanutlin. This design has 4.5% type I error rate at response rate of 25%, and 90% power if the true "response" rate is 50% or higher. At the end of stage I, patient accrual will not be halted; accrual will be stopped after the data from the 16th patient are available and the number of responders is below the threshold. The patients who are already accrued at the time of interim decision will be followed and their data will be included in all the subsequent analysis.

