## 25. Reporting and Exclusions

All patients included in the study must be assessed for safety, tolerability, and response to treatment, even if there are major protocol treatment deviations or if they are ineligible. Each patient will be assigned one of the following categories: 1) complete response, 2) partial response, 3) stable disease, 4) progressive disease, 5) early death from malignant disease, 6) early death from toxicity, 7) early death because of other cause, or 9) unknown (not assessable, insufficient data). All of the patients who met the eligibility criteria (with the possible exception of those who received no study medication) should be included in the main analysis of the response rate. Patients in response categories 4-9 should be considered to have a treatment failure (disease progression). Thus, an incorrect treatment schedule or drug administration does not result in

exclusion from the analysis of clinical endpoints (e.g. overall response rate and clinical benefit rate).

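### Section 24.3.1 names no analysis set for the 16-week PFS test, and Sections 7.10 and 7.12 conflict with 7.11 and 25 on which treated patients count

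*Combined protocol and SAP*

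**What the plan says.** Section 24.3.1 makes 16-week PFS (yes/no) the primary endpoint, labels it a response, and plans the following: "16-week PFS and 8-week PFS) will be estimated and reported along with a 95% exact confidence interval". An arm stops at 4 or fewer successes in 16 and succeeds at 13 or more in 33. On error it says "This design has 4.5% type I error rate at response rate of 25" percent, with 90% power at 50%. Its only inclusion statement is that patients already accrued at the interim decision stay in later analyses. It cites none of the sections below.

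- **7.10:** "all patients who initiate protocol treatment and receive at least 8 weeks of treatment will be included in overall evaluation of response".
- **7.11:** patients who stop for non-compliance or unacceptable toxicity remain in the evaluation of safety and response, with no minimum exposure. For those who leave at their own request: "These patients will be included in the overall evaluation of safety and response if any protocol therapy was administered prior to withdrawal".
- **7.12:** a patient who stops for reasons clearly unrelated to treatment, with less than one cycle and/or under 75% of the cycle 1 dose, is "considered not evaluable for efficacy analysis (will still be included in the safety analysis though) and may be replaced with a new patient".
- **25:** eligible patients, possibly except those never dosed, belong in the main response-rate analysis. "Patients in response categories 4-9 should be considered to have a treatment failure (disease progression"). The categories include early death and unknown. The endpoints it names are response rate, overall response rate and clinical benefit rate.
- **24.1:** at least 6 patients are treated at the recommended phase II dose of idasanutlin. "These patients will also be considered evaluable in the phase II portion of the study".

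**The concern.** In a single-arm test with a fixed cut-off of 13 in 33, who is counted is part of the test. One or two classification decisions can move an arm across the boundary, and in an open-label trial they could be made after the outcome is known. Sections 7.10 and 7.12 both act on patients who leave early, the group in which 16-week failures may be concentrated. Applied to the primary test, they could remove failures that Section 25 would count. The stakes are the type I error if removed failures are replaced, and the reported 16-week rate and its exact interval if they are only dropped.

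**Working it through.** **1. The plan's own figures.** Inputs from 24.3.1: n1 = 16, stop at ≤4; n = 33, succeed at ≥13; p0 = 0.25, p1 = 0.50.

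P(success | p) = Σ over x = 5 to 16 of P(Bin(16, p) = x) × P(Bin(17, p) ≥ 13 − x).

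- p = 0.25: 0.0449 (stated 4.5%)
- p = 0.50: 0.9017 (stated 90%)
- Stage I stop at p = 0.25: P(Bin(16, 0.25) ≤ 4) = 0.630

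The stated figures are reproduced.

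**2. One patient under each rule.** Take a dosed patient who withdraws in week 3, at her own request, for a reason unrelated to treatment.

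| Section | Status |
|---|---|
| 7.10 | outside the 8-week group |
| 7.11 | included |
| 7.12 | not evaluable, may be replaced |
| 25 | failure, if not assessable |

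Sections 7.11 and 25 agree in keeping her. Section 7.12 cannot be squared with them.

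**3. Replacement under 7.12.** If those replaced have the same chance of 16-week success as the rest, the null rate stays at 0.25 and type I error stays at 4.49%. If k early failures are replaced, on average, per 33 counted, the null rate among counted patients is 0.25 × (33 + k)/33. The documents give no k, so these values are assumptions.

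| k | Null rate | Type I error | Stage I stop, null arm |
|---|---|---|---|
| 0 | 0.2500 | 4.5% | 63.0% |
| 1 | 0.25 × 34/33 = 0.2576 | 5.6% | 60.3% |
| 2 | 0.25 × 35/33 = 0.2652 | 6.8% | 57.5% |
| 4 | 0.25 × 37/33 = 0.2803 | 9.9% | 52.0% |

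The last row is an outer case. Study calendar note 4 puts the first scheduled re-scan at 7 to 8 weeks, so a failure within cycle 1 would have to come from clinical progression, an unscheduled scan or death.

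**4. Exclusion under 7.10 without replacement.** Dropping failures adds no successes. With 33 enrolled and 13 still required, the most that can be lost is the stage I stop, so type I error is at most P(Bin(33, 0.25) ≥ 13) = 0.0484. The estimate does move. For illustration, 8/33 = 24.2% (95% exact CI 11.1 to 42.3) becomes 8/29 = 27.6% (12.7 to 47.2) if 4 early failures are dropped.

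**5. Cost of counting non-assessable patients as failures.** Assuming non-assessability is unrelated to outcome:

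- 5%: success rates 0.25 × 0.95 = 0.2375 and 0.50 × 0.95 = 0.475; type I error 3.1%, power 84.5%.
- 10%: success rates 0.225 and 0.45; type I error 2.0%, power 77.0%.

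**The case against.** Much of the case against stands.

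- **7.10 never says only.** It says patients with 8 weeks of treatment are included, and 7.11 can be read as adding others. The upward bias in step 4 therefore depends on reading 7.10 as an exclusion. But a threshold that excludes nobody has no purpose, and the text does not say which reading applies.
- **7.12 is narrow.** It is optional, requires a reason clearly unrelated to treatment, and opens by treating progression as the planned end of therapy. Exits unrelated to outcome are its natural target, and for those type I error is unchanged. Still, it does not say that early progression or death from disease never qualifies. The retention notes in 7.11 also do not extend to progression, intercurrent illness or a change in the patient's condition.
- **Section 25 nearly answers the question.** Since 24.3.1 labels 16-week PFS a response, a cross-reference might do. But Section 25 does not name that endpoint, and 7.12 would still contradict it.
- **Off-treatment follow-up continues.** Section 7.9 and calendar note 7 follow patients who stop for other reasons until progression, with scans every 8 to 9 weeks. Many early leavers can therefore have a known 16-week status, which limits the power cost.

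A reader might also infer that Section 12.1 conflicts, since it counts "Only those patients who have measurable disease present at baseline, have received at least one cycle of therapy, and have had their disease re-evaluated". That definition is for objective response in measurable disease and does not govern 16-week PFS. Nor do the documents support calling the 25% null the rate in all treated patients: 24.3.1 derives it from a reported 8-week median and does not give the historical analysis set.

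**Conclusion.** The gap and the conflict are real and should be fixed. Section 24.3.1 has no analysis set, and at least one ordinary kind of patient is kept, replaced or counted as a failure depending on the section applied.

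A reader might infer that the stated 4.5% is wrong or that the plan inflates it. The documents do not support that. The figure is exact for the design. It holds when every patient's 16-week status is counted, or when removals are unrelated to outcome, and it falls if non-assessable patients count as failures. Inflation requires that early failures be replaced under an unlikely reading of 7.12: about 5.6% for one and 6.8% for two per 33 counted, on assumed counts. No other section permits replacement on account of early exit from treatment. Under an excluding reading of 7.10, the harm is to the estimate and its interval, not to the error rate.

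Confidence is high on the textual inconsistency. The inflation is conditional. The Phase Ib carry-over concerns the idasanutlin arm only. Its effect is not quantified here, because the plan does not say whether those patients are among the 16 and 33.

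**What to change.** In 24.3.1:

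1. Define the primary set as all eligible patients in the arm who received at least one dose. Count progression, death or no 16-week assessment as failure, in line with Section 25.
2. Use the off-treatment scans under 7.9 and calendar note 7 to establish 16-week status before calling a patient non-assessable.
3. State that 7.10 and 7.12 neither remove nor replace patients in this test, and reconcile both with 7.11 and Section 25.
4. State whether the Phase Ib patients treated at the recommended phase II dose count toward the 16 and the 33 in the idasanutlin arm.
5. Report any evaluable-patient analysis as a labelled sensitivity analysis only.

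This changes wording only; the sample size and boundaries stay. The price is power: from 90.2% to about 84.5% with 5% non-assessable and 77.0% with 10%, under the assumption in step 5. Complete off-treatment scanning keeps that loss small.

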#### 7.12. **Replacement of Patients Who Discontinue Early**

In general, the study intends that patients would be treated until disease progression or intolerable toxicity. If a patient discontinues study treatment for reasons clearly not related to study treatment, after completing fewer than one planned cycle of study, and/or receiving <75% of the total intended dose of study drugs over the first cycle of treatment, then that patient will be considered not evaluable for efficacy analysis (will still be included in the safety analysis though) and may be replaced with a new patient.

#### 7.13. Withdrawal from Study

□ Subject withdraws consent for follow-up. □ Subject is lost to follow-up.	Th	The reasons for withdrawal from the study include:			
Study is terminated for any reason		•			

## 8. EXPECTED TOXICITIES AND DOSING DELAYS/DOSE MODIFICATIONS

## 8.1. Cobimetinib

## 8.2. Anticipated Toxicities

Ν	Most	common	adverse	events	from (	`∩.`	hime	tinik	າ inc	hul	Θ.
ľ	งเบรเ	CONTINUE	auveise	CVCIIIS	HUHH	ノし	MILLE	LIIIL	טווו ע	ıuu	┖.

Rash
Diarrhea
Nausea and vomiting
Anorexia
Fatigue
Peripheral edema
Visual disturbances
Hemorrhage
Elevation of CPK and rhabdomyolysis

## 8.2.1. Toxicity Considerations

#### Dermatologic toxicity 8.2.1.1.

Skin toxicities of rash have been reported in patients treated with Cobimetinib as a single agent or in combination with other therapies. In the Phase III study (GO28141), combined rash events of all types and grades were reported more frequently in patients treated with vemurafenib + Cobimetinib than vemurafenib + placebo (71.7% vs. 65.7%), although Grade ≥ 3 events (approximately 16%) and types of rash reported were similar between study arms. Specific events in patients treated with vemurafenib + Cobimetinib included rash (39% all grades, 5.9% Grade ≥ 3, 1.6% serious events) and rash maculo-papular (14.6% all grades, 6.3% Grade ≥ 3, 1.2% serious events). In the Phase I single-agent study (MEK4592g), reported rash events included rash (49.6% all grades, 4.3% Grade≥3 events) and rash maculo-papular (1.7% all grades, 0.9% Grade≥3 events).

The appearance of rash and other dermatologic events will be specifically closely monitored. Patients and investigators will be instructed to monitor closely for the development of rash. Patients will also be instructed to avoid sun exposure and to use sunscreen regularly while receiving study treatment. Prophylactic therapy for rash is not allowed prior to a first event of rash in this study; exceptions may be granted with the approval of the Medical Monitor. Patients must seek further evaluation promptly if rash develops.

Patients who develop Grade 1-2 skin toxicity may be treated with concomitant medications (e.g., topical agents, oral antibiotics, topical moisturizers for dry skin) at the discretion of the investigator. Patients who experience clinically significant acneiform rash should be treated with standard therapies for EGFR-related toxicity, for example topical tetracycline, topical clindamycin, topical silver sulfadiazine, diphenhydramine or a similar antihistamine, and/or oral antibiotics (e.g., tetracycline, doxycycline, minocycline). Treatment of rash should be initiated early (i.e., at onset of symptoms).

